2.6.3.3 Anti-pseudomonal antibiotics

Proportion of patients requiring anti-pseudomonal antibiotics

The proportion of patients requiring anti-pseudomonal antibiotics across the treatment epoch and across the entire study period will be summarized by treatment arm and by route of administration (overall, oral and parenteral).

Time to first use of anti-pseudomonal antibiotics across the entire study period

The time to first use of anti-pseudomonal antibiotics by route of administration (overall, oral and parenteral) will be analyzed using a Cox regression model stratified by baseline macrolide use. The model will include treatment as a fixed-effect factor, and number of pulmonary exacerbations in the 12 months prior to screening as a covariate. Six pairwise comparisons will be evaluated as specified in [Section 2.6.3](#). in addition two pairwise comparisons will be evaluated between pooled continuous regimens vs pooled placebo and, between pooled cyclic regimens and pooled placebo. The estimated adjusted hazard ratio for TIP over placebo will be displayed along with the associated 2-sided 95% CI.

The exposure adjusted rate of usage of anti-pseudomonal antibiotics across the entire study period

The number of anti-pseudomonal antibiotics across the entire study period will be analyzed by route of administration (overall, parenteral and oral) using a generalized linear model assuming the negative binomial distribution including treatment and baseline macrolide use as fixed-effect factors, and number of pulmonary exacerbations in the 12 months prior to screening as a covariate. The log time in study in years will be included as an offset variable in the model. Six pairwise comparisons will be evaluated as specified in [Section 2.6.3](#), in addition two pairwise comparisons will be evaluated between pooled continuous regimens vs pooled placebo and, between pooled cyclic regimens and pooled placebo. The adjusted rate of usage will be provided for each treatment arm. The estimated rate ratio together with the 2-sided 95% interval will be provided.

Duration of anti-pseudomonal antibiotic use across the entire study period

The duration of anti-pseudomonal antibiotic use (days) across the entire study period will be summarized by cohort, treatment arm and pooled cyclic and continuous regimens and by route of administration (overall, parenteral and oral).

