9.5 Analysis of secondary variables

9.5.1 Efficacy variables

For efficacy analysis, patients assigned to placebo arms will be pooled across the 3 cohorts, as the number of placebo capsules is not expected to impact the efficacy assessments. Unless otherwise specified, the following analysis will be conducted both over the treatment epoch (through Day 113) and over the study period (through Day 169).

9.5.1.1 *P. aeruginosa* colony forming units (CFU)

Anti-microbial efficacy of TIP versus placebo over the entire study duration, as measured by the absolute change in *P. aeruginosa* colony forming units (CFU) in sputum from baseline to each post-baseline visit, other than Visit 103, will be assessed by biotype and sum of all biotypes with the same ANCOVA model as specified for the primary efficacy variable.

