9.5.1.3 Anti-pseudomonal antibiotics

Time to first use (overall, oral, and parenteral) of anti-pseudomonal antibiotics will be analyzed using Cox regression model stratified by baseline macrolide use. The model will include treatment, cohort as fixed-effect factors, and number of pulmonary exacerbation in the 12 months prior to screening as covariate.

Rate of usage (overall, oral, and parenteral) of anti-pseudomonal antibiotics will be analyzed using a generalized linear model assuming the negative binomial distribution including treatment, cohort, baseline macrolide use as fixed-effect factors, and number of pulmonary exacerbation in the 12 months prior to screening as covariate. The log exposure in years will be included as an offset variable in the model.

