9.5.1.4 Hospitalization

Time to first hospitalization and the rate of hospitalization due to serious respiratory-related AEs will be analyzed using the same models as specified for the pulmonary exacerbation.

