To evaluate the effect of different doses of TIP on the change in P. aeruginosa bacterial load in sputum at Day 29	Change from baseline to Day 29 in P. aeruginosa density in sputum (log ₁₀ CFUs)	Section # 2.5.2
To assess the safety and tolerability with different doses of TIP and different regimens, on treatment epoch and over entire study duration	Safety: incidence rate of AEs/Serious AEs by MedDRA primary SOC and PT terms Tolerability: incidence and severity of local AEs (eg. cough, bronchospasm, dysgeusia, dry mouth, etc.)	2.7.1
Secondary		
To assess the antimicrobial efficacy of TIP over the entire study duration	Change from baseline to each post-baseline visit in P. aeruginosa density in sputum (log ₁₀ CFUs)	2.6.3.1
To assess the effect of different doses of TIP and different regimens on pulmonary exacerbation at the end of treatment epoch (Day 113) and over the study period	Time to first pulmonary exacerbation by exacerbation category Duration of pulmonary exacerbations by exacerbation category Exposure adjusted rate of exacerbations Proportion of patients with at least one pulmonary exacerbation by exacerbation category Proportion of patients who permanently discontinued study drug due to pulmonary	2.6.3.2

[figure not shown]
Objective	Endpoint	Statistical Analysis
To assess the efficacy profile of different doses of TIP and different regimens as measured by anti-pseudomonal antibiotics usage during the treatment epoch (through Day 113) and the study period	exacerbation Time to permanent study drug discontinuation due to pulmonary exacerbation Time to first use (overall, oral, and -parenteral) of anti-pseudomonal antibiotics usage	2.6.3.3
To assess the hospitalization (other than those regularly scheduled hospitalization that were planned prior to study start)	Proportion of patients used anti-pseudomonal antibiotics usage Duration of anti-pseudomonal antibiotics usage Time to first hospitalization due to serious respiratory-related AEs Number of hospitalizations due to serious respiratory-related AEs Proportion of patients requiring hospitalization due to serious respiratory-related AEs	2.6.3.4
To evaluate the safety profile of TIP in terms of clinical laboratory results	Duration of hospitalization due to serious respiratory-related AEs Laboratory results (hematology, serum chemistry, urine dipstick tests): means, mean changes from baseline, frequency/shift tables by visit	2.7.3

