2.6 Analysis of secondary and exploratory efficacy objective(s)

For efficacy analysis, patients assigned to placebo arms will be pooled across the 3 cohorts, as the number of placebo capsules is not expected to impact the efficacy assessments. Unless otherwise specified, the following analysis will be conducted both over the treatment epoch (through Day 113) and over the entire study period (through Day 169).

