2.6.1.4 Hospitalization

The following hospitalization-related parameters will be assessed by cohort and treatment arm, by pooled three continuous TIP regimens and pooled three cyclic TIP/placebo regimens:

- Time to first hospitalization due to serious respiratory-related AEs across the entire study period
- Duration of hospitalization due to serious respiratory-related AEs across the entire study period
- Number of hospitalizations due to serious respiratory-related AEs across the entire study period
- Proportion of patients requiring hospitalization due to serious respiratory-related AEs across the entire study period

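### The SAP labels the antibiotic-use and respiratory-hospitalisation models as whole-study only; the treatment-epoch models planned in Protocol 9.5.1 should be restored beside them

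*SAP*

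**What the plan says.** Protocol 9.5.1 sets a default for secondary efficacy, subject to being specified otherwise: "the following analysis will be conducted both over the treatment epoch (through Day 113) and over the study period (through Day 169". The two endpoint sections that follow do not depart from it. Protocol 9.5.1.3 states "Time to first use (overall, oral, and parenteral) of anti-pseudomonal antibiotics will be analyzed using Cox regression model stratified by baseline macrolide use" and adds a negative binomial model for the rate of use, with no window named. Protocol 9.5.1.4 says that time to first hospitalisation and the hospitalisation rate "will be analyzed using the same models as specified for the pulmonary exacerbation", again with no window.

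SAP 2.6 carries the same default with the same qualifier: "the following analysis will be conducted both over the treatment epoch (through Day 113) and over the entire study period (through Day 169". SAP Table 1-1 phrases the antibiotic objective "as measured by anti-pseudomonal antibiotics usage during the treatment epoch (through Day 113) and the study period". Its hospitalisation row names no window.

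The detailed SAP sections are narrower. SAP 2.6.1.3 and 2.6.3.3 put the time-to-first-use and rate analyses under whole-study headings, for example "Time to first use of anti-pseudomonal antibiotics across the entire study period". SAP 2.6.1.4 lists "Time to first hospitalization due to serious respiratory-related AEs across the entire study period", and the hospitalisation rate model in 2.6.3.4 is for the study period. For the treatment epoch the SAP keeps the proportion of patients using antibiotics (2.6.3.3), and the proportion hospitalised with the number of events (2.6.3.4).

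**The concern.** The follow-up epoch is eight weeks without study drug (Protocol 5.2). Protocol 3.3 gives its purpose as learning whether clinical effects persist. Two windows answer two questions: what happens on treatment, and what remains afterwards. A single whole-study ratio mixes them. If the effect weakens after Day 113, the whole-study ratio understates the on-treatment effect, and nothing model-based is left to show it.

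Antibiotic use has a further problem. Protocol 5.5.7 permits pre-planned prophylactic systemic antibiotics only during follow-up, so whole-study counts can include courses that do not reflect need during treatment. The documents give no figure from which to size this.

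**Working it through.** **The plan's own figures.** Neither document gives an event rate, effect size or power for these endpoints. The one power statement (Protocol 9.7, SAP Section 3) concerns the Day 29 CFU comparison. It reproduces: 48 and 36 patients less 20% are 38.4 and 28.8, and with difference 2.0, SD 2.0 and two-sided alpha 1.67% a noncentral t calculation gives 94.2% against the stated 94%. It does not bear on this point.

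**Windows side by side.**

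| Analysis | Protocol | SAP |
|---|---|---|
| Antibiotic use, Cox | both (9.5.1 default) | whole study (2.6.1.3, 2.6.3.3) |
| Antibiotic use, negative binomial | both | whole study (2.6.1.3, 2.6.3.3) |
| Hospitalisation, Cox | both (9.5.1 with 9.5.1.4) | whole study in 2.6.1.4; text of 2.6.3.4 names none |
| Hospitalisation, negative binomial | both | study period (2.6.3.4) |
| Exacerbation rate and duration, for comparison | both | both (2.6.3.2) |

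**Share of time off drug.** 56 / (112 + 56) = 56/168 = 33.3%.

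**Dilution of a rate ratio, continuous arms.** Assume a constant background rate. Whole-study ratio = (112 × RR on drug + 56 × RR off drug) / 168.

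- No persistence (RR off = 1): 0.60 gives (67.2 + 56)/168 = 0.733; 0.50 gives (56 + 56)/168 = 0.667; 0.70 gives (78.4 + 56)/168 = 0.800.
- Half the log effect persists (0.60 on drug, √0.60 = 0.775 off): (67.2 + 43.4)/168 = 0.658.
- Full persistence: 0.600, no dilution.

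**Cyclical arms.** If the effect exists only on active days, 0.60 becomes (56 × 0.60 + 56)/112 = 0.80 through Day 113 and (56 × 0.60 + 112)/168 = 0.87 over the whole study. The placebo cycles lie inside the treatment epoch, so a Day 113 model removes only the second step.

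**Cox model.** Taking the limiting hazard ratio under piecewise-constant hazards, with assumed control rates from 3 down to 0.2 per year and no persistence, 0.60 becomes 0.68 to 0.73 and 0.50 becomes 0.61 to 0.66. First events fall early, so dilution is smaller than for the rate model; at the lowest rate it is nearly the same.

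**Illustrative power.** Pooled continuous arms against pooled placebo at planned size (72 v 36), two-sided 5%. Two events per year, a ratio of 0.5 and dispersion 0.5 are assumptions.

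| Model | Through Day 113 | Whole study, no persistence | Half of log effect | Full |
|---|---|---|---|---|
| Cox | 54% | 40% | 55% | 67% |
| Negative binomial | 55% | 32% | not computed | 68% |

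With 107 randomised, the same arms hold about 107 × 72/180 = 43 and 107 × 36/180 = 21 patients. Cox power is then about 35% through Day 113, against 26% (no persistence) to 45% (full persistence) over the whole study.

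**Offset in the hospitalisation rate model.** SAP 2.6.3.4 counts events over the study period but offsets by log treatment exposure; the antibiotic model in 2.6.3.3 uses log time in study. For a completer, the time in which events count is 168/112 = 1.5 times the offset time. For an illustrative patient who stops drug on Day 28 and then completes 56 days of follow-up it is 84/28 = 3 times. Unequal early discontinuation between arms would therefore distort the rate ratio.

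**The case against.** The strongest reply is that the default in both documents yields where something else is specified, and the detailed SAP sections do specify a window. That settles how to read the SAP, but not its difference from the protocol, whose own antibiotic and hospitalisation sections make no exception, nor its conflict with SAP Table 1-1 for antibiotics.

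Second, this may be loose drafting. SAP 2.6.1.2 lists time to first exacerbation for the overall study, yet 2.6.3.2 gives censoring rules for both windows; 2.6.4 has a generic treatment-period censoring rule; and the hospitalisation Cox text names no window. That is fair for the Cox models. The rate models are more plainly whole-study.

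Third, a reader might infer that every effect is diluted and that proportional hazards must fail. The documents do not support this. Both need the effect to fade after Day 113, and follow-up is there to find out. The cited inhaled-gentamicin study lost its effect after three months off drug; follow-up here is eight weeks. With full persistence the whole-study model is the more powerful one, and it was itself planned.

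Fourth, it is tempting to say that the SAP drops all treatment-epoch analysis or hides the change. It keeps the descriptive summaries listed above, and the hospitalisation Kaplan-Meier curves can be read at Day 113. The visible text of SAP Section 4 gives no reason for the narrowing, but the contents list shows a blacked-out entry directly after that section, so silence proves nothing.

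Finally, materiality: the endpoints are secondary and unadjusted, and SAP Section 1 allows all inference to be considered exploratory at 107 patients. This stands and limits the weight of the point.

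**Conclusion.** The point holds as a gap between protocol and SAP. All four inferential analyses (Cox and negative binomial, for antibiotic use and respiratory hospitalisation) are labelled whole-study only, where the protocol plans them for both windows. The missing piece is the on-treatment estimate; the whole-study analysis is not wrong in itself. Its cost depends on persistence, which is unknown: a rate ratio of 0.60 on drug reads as 0.73 with no persistence, 0.66 if half the log effect persists and 0.60 if all of it does, given a constant background rate. The 33% off-drug share is firm. The tempting figure of two thirds of days off active drug in the cyclical arms is arithmetically right, (56 + 56)/168, but half of it is placebo cycles that a Day 113 model would also contain. Exploratory status puts the weight on estimates rather than tests, which is a reason to report the missing one, with no expectation of a decisive result.

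**What to change.** - In SAP 2.6.3.3 and 2.6.3.4, add the same Cox and negative binomial models for events through Day 113, with time at risk to the earlier of Day 113 and last contact. State this explicitly, because 2.6.4 would otherwise censor treatment-period analyses at last dose. Keep the whole-study versions.
- Keep the existing rule in 2.6.3.4 that only Kaplan-Meier estimates are given if hospitalisations are few, and apply it to the Day 113 window too.
- Align 2.6.1.3 with SAP Table 1-1, and 2.6.1.4 with Protocol 9.5.1.
- In the study-period hospitalisation model, replace the offset of log treatment exposure by log time in study, as in 2.6.3.3.

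The cost is SAP wording, programming and tables; no new data are needed. The output is not trivial. With eight comparisons, three routes by two antibiotic models, and two hospitalisation models, it adds 8 × (3 × 2 + 2) = 64 unadjusted exploratory estimates, many resting on few events. They should be presented as estimates with intervals and read in that light.

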2.6.3.4 Hospitalization

Proportion of patients requiring hospitalization due to serious respiratory-related AEs

The proportion of patients requiring hospitalization due to serious respiratory-related AEs across the treatment period, follow up period, and across the entire study period will be summarized by treatment arm and by pooled continuous and cyclic regimen. The number of events will also be summarized.

The time to first hospitalization due to serious respiratory-related AEs

The time to first hospitalization due to serious respiratory related AEs will be analyzed using a Cox regression model stratified by baseline macrolide use. The model will include treatment as a fixed-effect factor, and number of pulmonary exacerbations in the 12 months prior to screening as covariate. Six pairwise comparisons will be evaluated as specified in [Section 2.6.3](#), in addition two pairwise comparisons will be evaluated between pooled continuous regimens vs pooled placebo and, between pooled cyclic regimens and pooled placebo. The estimated adjusted hazard ratio for TIP over placebo will be displayed along with the associated 2-sided 95% CI.

Kaplan-Meier analysis stratified by treatment arm will be also presented and displayed graphically.

If a small number of events occur after pooling events, only the Kaplan-Meier estimation of time to first hospitalization due to serious respiratory-related AEs will be provided.

Duration of hospitalization due to serious respiratory-related AEs

The duration of hospitalization due to serious respiratory-related AEs (days) across the entire study period will be summarized by treatment arm [and](#) pooled arms by continuous and cyclic regimens. Summaries will be event driven and not patient driven.

Number of hospitalizations due to serious respiratory-related AEs

The number and percentage of patients with 0, 1, 2, >2 hospitalizations due to serious respiratory-related AEs across the entire study period will be summarized by treatment arm

[figure not shown]
and pooled arms by continuous and cyclic regimens.

The exposure adjusted rate of hospitalization due to serious respiratory-related AEs

The exposure adjusted rate of hospitalization due to serious respiratory-related AEs will be determined across the study period.

The number of hospitalization due to serious respiratory-related AEs during the study period will be analyzed using a generalized linear model assuming the negative binomial distribution including treatment and baseline macrolide use as fixed-effect factors, and number of pulmonary exacerbations in the 12 months prior to screening as a covariate. The log exposure to treatment in years will be included as an offset variable in the model.

Six pairwise comparisons will be evaluated as specified in [Section 2.6.3](#), in addition two pairwise comparisons will be evaluated between pooled continuous regimens vs pooled placebo and, between pooled cyclic regimens and pooled placebo. The estimated rate ratio along with 2-sided 95% interval will be provided.

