2.2 Secondary objectives

- To assess the effect of different doses of TIP administered o.d. and one b.i.d. dose and different regimens (TIP and TIP/placebo cyclical) on the frequency, rate (by patient-months), severity and time to onset of pulmonary exacerbations at the end of the treatment epoch and over the entire study, each compared to placebo.
- To assess the efficacy profile of different doses of TIP administered o.d. and one b.i.d. dose and different regimens (TIP and TIP/placebo cyclical), as measured by the time to first use, proportion of patients requiring anti-pseudomonal antibiotics (overall, oral, parenteral) and the duration of treatment of anti-pseudomonal antibiotics, each compared to placebo.
- To assess the time to first hospitalization, proportion of patients requiring hospitalization and the duration of hospitalization due to serious respiratory-related AEs (other than those regularly scheduled hospitalization that were planned prior to study start).
- To assess the pharmacokinetic concentrations of tobramycin in serum and in sputum from different doses of TIP administered o.d. and one b.i.d. dose and different regimens (TIP and TIP/placebo cyclical).
- To assess the antimicrobial efficacy of TIP over the entire study duration, as measured by the absolute change in *P. aeruginosa* colony forming units (CFU) in sputum from baseline to each post-baseline treatment visit and during the follow-up visits.
- To evaluate the safety profile of TIP in terms of clinical laboratory results.
- To evaluate the safety profile of TIP in terms of audiology findings throughout the treatment epoch (subgroup of all patients that are in enrolled at sites that are adequately equipped and trained to perform audiology assessments).
- To evaluate the safety profile of TIP in terms of acute change in forced expiratory volume at 1 second (FEV₁) % predicted values from pre-dose to 30±15 minutes after completion of study drug administration at the clinical site at visits during the treatment epoch.
- To evaluate the impact of treatment with TIP on the Respiratory Symptom Scale Quality of Life Questionnaire for Bronchiectasis (QOL-B) by measuring change from baseline to all post-baseline visits.

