1.2.2 Secondary objectives

- To assess the effect of different doses of TIP administered o.d. and one b.i.d. dose and different regimens (TIP and TIP/placebo cyclical) on the frequency, rate (by patient months), severity and time to onset of pulmonary exacerbations at the end of the treatment epoch and over the entire study, each compared to placebo.
- To assess the efficacy profile of different doses of TIP administered o.d. and one b.i.d. dose and different regimens (TIP and TIP/placebo cyclical), as measured by the time to first use, proportion of patients requiring anti-pseudomonal antibiotics (overall, oral, parenteral) and the duration of treatment, each compared to placebo.

[figure not shown]
- To assess the time to first hospitalization, proportion of patients requiring hospitalization and the duration of hospitalization due to serious respiratory-related AEs (other than those regularly scheduled hospitalization that were planned prior to study start).
- To assess the pharmacokinetic concentrations of tobramycin in serum and in sputum from different doses of TIP administered o.d. and one b.i.d. dose and different regimens (TIP and TIP/placebo cyclical).
- To assess the antimicrobial efficacy of TIP over the entire study duration, as measured by the absolute change in *P. aeruginosa* -CFUs in sputum from baseline to each post-baseline treatment visit and during the follow-up visits.
- To evaluate the safety profile of TIP in terms of clinical laboratory results.
- To evaluate the safety profile of TIP in terms of audiology findings throughout the treatment epoch (subgroup of all patients that are in enrolled at sites that are adequately equipped and trained to perform audiologic assessments).
- To evaluate the safety profile of TIP in terms of acute change in forced expiratory volume at 1 second (FEV₁) % predicted values from pre-dose to 30±15 minutes after completion of study drug administration at the clinical site at visits during the treatment epoch.
- To evaluate the impact of treatment with TIP on the Respiratory Symptom Scale Quality of Life Questionnaire for Bronchiectasis (QOL-B) by measuring change from baseline to all post-baseline visits.

[figure not shown]
Table 1-1 Primary and secondary objectives and related endpoints

Objective	Endpoint	Statistical Analysis
Primary		

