2.6.3 Statistical hypothesis, model, and method of analysis

In general, unless otherwise specified, the following 6 pairwise comparisons will be performed for the secondary endpoints at the 5% significance level without multiplicity adjustment, wherever an inferential analysis is specified:

- TIP 3 capsules OD versus pooled placebo
- TIP/placebo cyclical 3 capsules OD versus pooled placebo
- TIP 5 capsules OD versus pooled placebo
- TIP/placebo cyclical 5 capsules OD versus pooled placebo
- TIP 4 capsules BID versus pooled placebo
- TIP/placebo cyclical 4 capsules BID versus pooled placebo

Descriptive summary statistics by cohort, treatment arm, pooled treatment arm by regimen and pooled placebo will be provided where applicable.

In addition, data will also be summarized for selected endpoints, by pooling continuous TIP regimens together (i.e. TIP 3 capsules OD. from Cohort A + TIP 5 capsules OD from Cohort B+ TIP 4 capsules BID from cohort C) and pooling cyclic TIP regimens together (i.e. TIP/placebo cyclical 3 capsules OD from Cohort A + TIP/placebo cyclical 5 capsules OD. from Cohort B+ TIP/placebo 4 capsules BID cyclical from cohort C) vs pooled placebo.

In addition, the following 2 pairwise comparisons will be performed for the selected endpoints at the 5% significance level without multiplicity adjustment:

- Pooled TIP continuous regimens versus pooled placebo
- Pooled TIP/placebo cyclical regimens versus pooled placebo.

Forest plot will be plotted for below endpoints in addition to the primary endpoint for each treatment arm across 3 cohorts compared with pooled placebo separately and also for the comparison between pooled TIP continuous (pooled from 3 cohorts) with pooled placebo and for

the comparison between pooled TIP/placebo cyclic (pooled from 3 cohorts) with pooled placebo.

- LS Mean difference in log₁₀ CFUs of *P. aeruginosa* in sputum and CI
- For exposure adjusted rate and CI of pulmonary exacerbations during the study
- For incident rate ratio and CI for anti-pseudomonal antibiotics during the study
- Incident rate ratio and CI hospitalization due to serious respiratory-related AEs across the entire study period
- LS Mean difference in QoL-B RSS and CI

2.6.3.1 *P. aeruginosa* colony forming units (CFU)

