Six pairwise comparisons will be evaluated as specified in [Section 2.6.3](#), in addition two pairwise comparisons will be evaluated between pooled continuous regimens vs pooled placebo and, between pooled cyclic regimens and pooled placebo. The estimated rate ratio along with 2-sided 95% interval will be provided.

The exposure adjusted rate of exacerbations across the entire study period will be derived as follows:

(Number of patients with a pulmonary exacerbation during the study period / sum of study period duration for all patients during the study period) / 365.25.

The number of pulmonary exacerbations during the entire study period will be analyzed in a similar manner as the pulmonary exacerbations during the treatment period; the log time in study in years will be included as an offset variable in the model.

Duration of pulmonary exacerbations overall

The duration of pulmonary exacerbations is defined as the sum of the duration of days recorded as an exacerbation for all exacerbations recorded per patient. This will be derived across the treatment period and across the study period. The duration of pulmonary exacerbations will be analyzed using an ANCOVA model. The model will include treatment as a fixed-effect factor, and number of pulmonary exacerbations in the 12 months prior to screening as a covariate.

Six pairwise comparisons will be evaluated as specified in [Section 2.6.3](#), in addition two pairwise comparisons will be evaluated between pooled continuous regimens vs pooled placebo and, between pooled cyclic regimens and pooled placebo. The estimated adjusted treatment difference for each of the comparisons (TIP–placebo) will be displayed along with the associated standard error, 2-sided 95% CI.

Time to permanent study drug discontinuation due to pulmonary exacerbation

The proportion of subjects who permanently discontinue study drug to pulmonary exacerbation will be summarized by cohort and treatment arm.

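### Respiratory hospital duration is summarised per admission only, and no planned output shows hospital days per randomised patient

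*SAP*

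**What the plan says.** Protocol 2.2 includes "the duration of hospitalization due to serious respiratory-related AEs" in a secondary objective. SAP 1.2.2 repeats it as "proportion of patients requiring hospitalization and the duration of hospitalization due to serious respiratory-related AEs", and Table 1-1 lists duration as an endpoint.

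SAP 2.6.3.4 gives the analysis: lengths of stay over the whole study are tabulated for each arm and for the two pooled regimens. It then sets the unit of analysis: "Summaries will be event driven and not patient driven". No model, treatment difference or confidence interval is specified for duration, and neither document defines a per-patient total of hospital days.

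The parallel endpoint is handled differently. In SAP 2.6.3.2, exacerbation duration is "the sum of the duration of days recorded as an exacerbation for all exacerbations recorded per patient", analysed by ANCOVA with pairwise comparisons against pooled placebo.

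The other hospitalization analyses in SAP 2.6.3.4 are at patient level: proportion admitted, time to first admission, patients with 0, 1, 2 or more than 2 admissions, and a negative binomial rate.

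**The concern.** Admission happens after randomisation and may itself be changed by treatment. A mean taken over admissions describes the stays that occurred, in whichever patients had them. It does not compare the groups as randomised, because patients who stayed out of hospital contribute nothing and a patient with several stays contributes several times.

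Mean stay per admission and hospital burden per patient can therefore point in opposite directions. The trial is meant to inform the choice of dose and regimen (Protocol 1.2). A reader who takes the duration table as the answer to the duration part of the objective could draw the wrong conclusion about which arm spent less time in hospital.

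**Working it through.** The documents give no admission counts or lengths of stay, so there is no plan figure to reproduce. The admissions below are assumed, to show direction only.

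**Formulas.** For an arm with N patients, A admissions and D total hospital days:

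- days per admission (the SAP measure) = D / A
- days per patient, zeros included = D / N

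Remove k admissions of average length s. Days per patient always fall, by ks / N. Days per admission become (D − ks) / (A − k), which exceeds D / A exactly when s < D / A. The reversal therefore occurs when the prevented stays are shorter than the arm's average, and not otherwise.

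**Numbers.** N = 36 in each arm; this is the planned pooled placebo total in Protocol 3.2, used for both arms for simplicity.

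| Scenario | Stays | Total days | Days per admission | Days per patient |
|---|---|---|---|---|
| Control | 6 × 3 and 4 × 14 | 74 | 74/10 = 7.4 | 74/36 = 2.06 |
| Active prevents all 6 short stays | 4 × 14 | 56 | 56/4 = 14.0 | 56/36 = 1.56 |
| Active prevents 3 of 6 short stays | 3 × 3 and 4 × 14 | 65 | 65/7 = 9.3 | 65/36 = 1.81 |
| Active prevents the 4 long stays | 6 × 3 | 18 | 18/6 = 3.0 | 18/36 = 0.50 |

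In rows two and three the SAP measure rises while burden falls. In row four both fall.

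**Sensitivity.** With short stays of 2 to 5 days, long stays of 10 to 21 days and 25% to 100% of the short stays prevented, days per admission rose and days per patient fell in every case. The smallest rise was from 7.0 to 7.35 days (stays of 5 and 10 days, 25% prevented). The largest was from 9.6 to 21.0 days (stays of 2 and 21 days, all short stays prevented).

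**Repeat stays.** If the four 14-day stays in row three belonged to one patient, that patient would supply 4 of the 7 observations and 56 of the 65 days. The event-level SD would not show this.

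**What can be recovered.** SAP 2.1 requires n and mean for continuous data. If n is the number of admissions with a complete length, n × mean returns total days: 10 × 7.4 = 74 and 4 × 14.0 = 56. Dividing by arm size gives the last column. The between-patient SD and median cannot be recovered.

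**Actual size.** SAP section 1 reports 107 patients randomised. Under 1:1:1 and 2:2:1 allocation that is about 107 × 2/15 = 14 per TIP arm and 107/5 = 21 on pooled placebo, so a single long stay can dominate a per-admission mean.

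**The case against.** The case for leaving the plan alone has several good parts.

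- **Length of stay per admission is a legitimate reading of duration.** The SAP states its unit openly. The contrast with exacerbation duration is not a contradiction: Protocol 9.5.1.2 defined that variable as a per-patient sum and defined nothing similar for hospital stay. SAP 2.6.3.2 also does not say that patients without an exacerbation count as zero. This stands.
- **Never-admitted patients are missing from one table, not from the hospitalization analysis.** The proportion, time-to-first, count and rate analyses would show fewer admissions beside the mean stay. This stands in part: those outputs show whether and how often patients were admitted, and none shows days in hospital.
- **Total days follow from n × mean.** This stands. What is missing is a displayed per-patient summary with its spread, not all information on total days.
- **The table is descriptive and secondary.** The trial closed early, and SAP section 1 calls its inferential results exploratory. Nothing makes this table a criterion for dose selection. This stands and limits the weight of the point.

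A reader might also infer that a promised comparison of duration with placebo was dropped. The documents do not support that. The exacerbation and antibiotic objectives call for comparison with placebo, but the hospitalization objective does not. SAP 2.6.3 applies its pairwise comparisons only "wherever an inferential analysis is specified". Protocol 9.5.1.4 models two other measures: "Time to first hospitalization and the rate of hospitalization due to serious respiratory-related AEs will be analyzed using the same models" as for exacerbations.

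**Conclusion.** The point holds as a minor descriptive improvement. The only planned summary of hospital duration conditions on admission, excludes never-admitted patients and counts repeat stays separately, so it can move against hospital burden. No planned output shows hospital days per randomised patient with their spread.

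In the illustration, 7.4 against 14.0 days per admission goes with 2.06 against 1.56 days per patient. These figures rest wholly on assumed admissions and equal arms of 36. They show that a reversal is possible, not that it is likely or how large it would be in this trial.

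A reader might infer that an effective arm will look worse in this table. That goes too far: the direction depends on which admissions are prevented, and preventing the long stays takes the mean from 7.4 to 3.0 days.

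**What to change.** Add to SAP 2.6.3.4 a descriptive summary of total respiratory hospital days per FAS patient over the study period, scoring 0 for patients never admitted. Add total days per patient-year of time in study, so that unequal follow-up is visible. Show both by treatment arm, pooled regimen and pooled placebo. Keep length of stay per admission as a supplement, labelled as conditional on admission and with the numbers of admissions and of patients admitted. State how days are counted and how stays still open at last contact are handled.

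No new data are needed: Protocol 6.6.1 already records admission and discharge dates and total length of stay. The cost is a few lines of SAP text and one table. The drawback is that the data will be skewed with many zeros, so the median may well be 0 and the mean should be read with the SD, the range and the number admitted. No test or model is needed.
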